#### 7.3.5. Additional Analysis

The pairwise correlation of Baseline values between the primary exploratory biomarker (P-tau181 and NfL), and the above-mentioned scales and parameters (see Section 7.3.3) will be analyzed irrespective of the treatment group (not per treatment group).

For each of the primary exploratory biomarker (P-tau181 and NfL), an ANCOVA will be used to analyze the natural logarithm of percentage change from Baseline at Week 52. The ANCOVA model will be the same as for the primary outcome (see Section 7.3.2) and the two sensitivity analyses will be performed as well, one including subject's age and sex, as well as *ApoE4* carrier status and plasma sample age, and the second including MRI whole brain volume and  $^{18}\text{F}$ -FDG-PET temporal lobe glucose uptake. Additional analysis will be performed upon request.

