#### 2.9.4. Other Variables

Other assessments are:

- A single blood sample for Apolipoprotein E gene (*ApoE*) obtained from subjects who provide legally acceptable informed consent, collected at any time after eligibility for randomization and continued participation in the study has been confirmed but prior to Week 52.
- Other biomarkers will be analyzed as well. Their analysis is pre-specified in the separate Research Plan “TRx-237-039\_Secondary Research Plan\_Plasma Biomarker Analysis\_v2.2\_16Mar23”. The analysis to be performed is described in more detail in Section 7 of this SAP.
- MRI arterial spin labelling parameters will be provided in a subject data listing.

Sponsor:	TauRx Therapeutics Ltd.		
Protocol:	TRx-237-039		
Document Version No.:	3.0	Document Date:	07-JUN-2023

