### **4.2. Data Conventions**

Mean, median, standard deviation, standard error, Q1 and Q3 will be presented with one more decimal place compared to the raw data, and minimum and maximum will be presented with the same number of decimal places as the raw data. Percentages will be presented with one decimal place.

Wherever a calendar date is presented in a listing, the corresponding Study Day will be included, with Study Day defined as:

- date – first dose date + 1, where date >= first dose date
- date – first dose date, where date < first dose date

For listings including day 1 data with assessments collected prior to and after first study drug, a flag will be included for pre-dose assessments.

The following conversion factors will be used to convert days to months or years where applicable:

- 1 month = 30.4375 days
- 1 year = 365.25 days
- 1 week = 7 days

Additional data handling rules are as follows:

Sponsor:	TauRx Therapeutics Ltd.		
Protocol:	TRx-237-039		
Document Version No.:	3.0	Document Date:	07-JUN-2023

- Age (years) = year of informed consent – year of birth
- Weight values recorded in pounds will be converted to kilograms using the following formula:  
kilograms = pounds/2.2046
- Height values recorded in inches will be converted to centimeters using the following formula:  
centimeters = inches\*2.54
- Temperature recorded in Fahrenheit to Celsius:  $1^{\circ}\text{C} = (\text{°F} - 32)/1.8$
- Duration on study (weeks) = (Last visit date – randomization date + 1) / 7
- Duration on treatment (weeks) = (Last dose date – first dose date + 1) / 7
- (Absolute) Change from Baseline = Value at the time point – Baseline value
- Relative Change from Baseline = (Value at the time point – Baseline value) / Baseline value \* 100

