To calculate descriptive / inferential statistics for laboratory values containing values below/above the limit of quantification, the following general rule of thumb will be applied: each laboratory value below/above the limit of quantification will be imputed numerically to the nearest value below/above the limit, respecting the same number of decimal places than numerical values (e.g., if the number of decimal places=0, subtract/add 1 to the limit of quantification (LOQ); if the number of decimal places=1, subtract/add 0.1 to the LOQ, etc.). Is the LOQ already the lowest value larger than zero, the LOQ will be imputed numerically to the nearest value below the limit with one more decimal place (e.g., if the LOQ is 1, subtract 0.1 from the LOQ: 0.9). The subject data listings will not show the imputed value, but that the value is below or above the limit of quantification.

Partial dates will be reviewed and imputed (where possible) after the BDRM and before unblinding, potentially resulting in an Excel file, which will be provided to Cytel for the use in the analysis. Remaining cases (if existing), which are required for calculation, or cases for which no additional information is provided after the BDRM or if no file has been generated will be handled as follows:

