## 7. PLASMA BIOMARKER ANALYSIS

The analysis described in this section is based on version 2.2 from 16-MAR-2023 of the TRx-237-039 Secondary Research Plan “Plasma Biomarker Analysis”, in which a detailed background, scientific rationale, and sample size justification is given.

The following analysis are all exploratory of nature. The analyses stand on their own and corresponding nominal p-values will be reported and no correction for multiple comparisons will be conducted.

A subject data listing of the biomarkers will be provided.

The tau fragment analysis, which was introduced with the version 2.1 of the Secondary Research Plan, is based on a subset of pre-dose Baseline back-up PK plasma samples is not part of this SAP. This analysis will be performed by the University of Aberdeen (Scottish Biologics Facility).

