### 7.1. Biomarker

The initial analysis focuses on the following primary exploratory biomarkers, which will be analyzed in the framework of primary and secondary biomarker endpoints:

- Tau phosphorylated at residue 181 (P-tau181)
- Neurofilament light (NfL)

The null hypotheses for each of these biomarkers are, that there is no difference from Baseline to Week 52 visit within the HMTM group and that HMTM does not have an impact on change of the respective endpoint from Week 52 to Baseline compared to control. For correlations between biomarkers and between other clinical study endpoints (see Section 7.3.3), the null hypothesis is that there is no correlation between those.

The following potential biomarkers are ‘other’ exploratory biomarker research and will be analyzed analogously to the primary exploratory biomarkers upon request, with T-tau being planned to be analyzed with version 2.2 of the Secondary Research Plan:

- Tau phosphorylated at residue 231 (P-tau231)
- Core-proline tau
- Total tau (T-tau)
- Glial fibrillary acidic protein (GFAP)

There is no prior evidence to show that these biomarkers will show a pharmacodynamic response to treatment with HMTM nor any other approved or investigational drugs for AD. Given this, no hypotheses are provided, but the above null-hypothesis apply here as well.

Sponsor:	TauRx Therapeutics Ltd.		
Protocol:	TRx-237-039		
Document Version No.:	3.0	Document Date:	07-JUN-2023

---

For the avoidance of doubt, even in the cases where a clear hypothesis exists which direction the change should take, all tests will be conducted at the two-sided, 0.05 level of significance.

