#### 7.1.1. Biomarker Samples

The investigated (potential) biomarkers are pre-analyzed in different companies and institutions: P-tau 181 and P-tau231 (Medpace Inc.), NfL (Drug Development Solutions Ltd.), Core-proline tau (University of Aberdeen Good Laboratory Practice Test Facility), T-tau (University College London Consultants Ltd.), and GFAP (*to be decided*). Due to different processing schedules, the pre-processed data will be provided to Cytel in batches and therefor the statistical analysis will be performed in batches.

Plasma samples have been taken at Baseline, Week 4, Week 52, and Week 104 visits, on three occasions: pre-dose, approximately 1 to 2 hours post-dose, and approximately 4 hours post-dose.

The biomarker data analysis is based on back-up PK plasma samples taken pre-dose during the Baseline and Week 52 visits.

On a subject level: If the pre-dose sample is unavailable, the earliest available post-dose sample (first: 1-2 hours post-dose, second: 4 hours post-dose) will be used; and furthermore, if the back-up plasma sample is unavailable the residual primary PK plasma will be utilized instead, if available. If no proper sample is available, the value is set to missing. This means, the order of samples is as follows:

- Back-up sample: 1. Pre-dose, 2. 1-2 hours pose-dose, 3. 4 hours post-dose
- Residual primary sample: 4. Pre-dose, 5. 1-2 hours pose-dose, 6. 4 hours post-dose
- 7. "Missing"

The first sample which is available will be used for the analysis. This means, for the avoidance of doubt, the analysis will be performed based on all available samples, irrespective of the actual sample used. Thus, pre-dose versus post-dose samples as well as primary versus back-up samples will be used alike. The only relevant characteristic of the sample is, which is used in the analysis, if it is Baseline or Week 52 visit.

Possible reasons for unavailability of a plasma sample are:

- More than one previous freeze-thaw cycle.
- An approximate hemoglobin concentration of 250 mg/dL or more.
- Incorrect collection of a sample.

For completeness, a summary table will be provided, that shows the number of samples used for each biomarker presented by treatment group and total, that were Baseline pre-dose, Baseline 1-2 hours post-dose, Baseline 4 hours post-dose, Week 52 pre-dose, Week 52 1-2 hours post-dose, and Week 52 4 hours post-dose. If needed, this will be further separated by back-up sample and primary sample.

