## 7.3. Statistical Analysis of Biomarker Outcomes

The following analysis will be performed based on the Biomarker Population.

Week 52 samples taken after the first day of the open-label treatment phase will not be used in the analysis.

Since from protocol version 5 on, the control group had occasional spiking with 4mg MTC with an average frequency of twice per week, it is therefore of interest to test not only the doses of HMTM compared to control, but also to a subpopulation of control that showed lowest predicted concentrations of parent MT at Week 52. A threshold of  $\leq 0.1$  ng/mL for predicted Week 52 steady-state ( $C_{max,ss}$ ) parent MT concentration will be used to define the lowest parent MT group. In the analysis output the control group will be presented as "MTC 8 mg/week".

The actual received treatment and the actual (verified) values of the randomization stratification variables will be used in the analysis.

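### The log of percentage change in P-tau181 and NfL (SAP 7.3.5) does not exist for a subject whose biomarker is unchanged or falls, and the SAP has no rule for such subjects

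*SAP*

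**What the plan says.** SAP Section 7.3.5 adds an analysis of the two primary exploratory biomarkers, P-tau181 and NfL, in which "an ANCOVA will be used to analyze the natural logarithm of percentage change from Baseline at Week 52". It reuses the Section 7.3.2 ANCOVA and adds two sensitivity models. It gives no formula for the outcome and no sample code.

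The only percentage-scale change formula in the SAP is in Section 4.2, which begins "Relative Change from Baseline = (Value at the time point" and continues by subtracting the Baseline value, dividing by it and multiplying by 100.

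Two other rules come near the question without covering it. For assay limits, Section 4.2 says "each laboratory value below/above the limit of quantification will be imputed numerically to the nearest value below/above the limit". For sample selection, Section 7.1.1 says "If no proper sample is available, the value is set to missing".

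On status, Section 7 states "The following analysis are all exploratory of nature", with nominal p-values and no multiplicity correction. Section 2.9.4 says of the biomarkers: "Their analysis is pre-specified in the separate Research Plan". Section 7 is based on version 2.2 of that plan.

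**The concern.** A logarithm needs a positive argument, and a signed percentage change is positive only when the marker rises. Stable or falling subjects are not a remote possibility: the within-group null in Section 7.1 is "that there is no difference from Baseline to Week 52 visit within the HMTM group", and the tests are two-sided. The outcome cannot score the very subjects who would show stability or benefit.

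Section 7.3 says "The following analysis will be performed based on the Biomarker Population". If undefined values become missing and are dropped, which is what software does by default, this analysis instead compares subsets of that population chosen by their outcome. The share lost can differ by arm, so randomization no longer protects the comparison.

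Two features make the gap worth closing. Section 7.4 lets an apparent benefit on any biomarker trigger further sample analysis, without saying which model decides. And according to the modification history and Section 10, the biomarker section entered in SAP version 3.0, after partial unblinding of the study team. A choice among dropping, offsetting and using a ratio should not stay open at that stage.

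**Working it through.** The SAP states no figure for this analysis, so there is none to reproduce.

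**Step 1. Apply the Section 4.2 formula.** r = (Week 52 − Baseline) / Baseline × 100. With an example Baseline of 20:

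| Week 52 | r | ln r | ln(Week 52 / Baseline) |
|---|---|---|---|
| 25 | 25 | 3.219 | 0.223 |
| 20.2 | 1 | 0 | 0.010 |
| 20 | 0 | undefined | 0 |
| 19 | −5 | undefined | −0.051 |
| 15 | −25 | undefined | −0.288 |

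Zero on the ln r scale means a 1% rise. No change, the value named in the within-group null, has no place on that scale.

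**Step 2. Look for a repair in the SAP.** The limit-of-quantification rule changes single assay values beyond the limit. The sample rule decides which specimen is used. The Section 7.3.2 sample code models untransformed change from Baseline. None of these deals with a non-positive change.

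**Step 3. Share of subjects with no value (assumption).** If ln(Week 52 / Baseline) is normal with mean m and SD s, the share is Φ(−m/s). For m = 0 it is 50%. For s between 0.15 and 0.30 it is 25% to 37% at m = +0.10, and 63% to 75% at m = −0.10.

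**Step 4. Effect on the arm comparison (assumption).** Let the percentage change X be normal in each arm, in units of the control SD. The unit does not matter, because rescaling X only adds a constant to ln X. Lost share = P(X ≤ 0). Standardized difference = (control mean − HMTM mean) / √(average of the two variances).

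Selection alone, raw scale, control N(0.5, 1) against HMTM N(0, 1), by the truncated-normal formulas:

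- Control, kept: mean 0.5 + 0.3521/0.6915 = 1.009; variance 1 − 0.5 × 0.509 − 0.509² = 0.486.
- HMTM, kept: mean 0.3989/0.5 = 0.798; variance 1 − 0.798² = 0.363.
- Difference: (1.009 − 0.798) / √((0.486 + 0.363)/2) = 0.211/0.652 = 0.324, against a true 0.500. The loss is 1 − 0.324/0.500 = 35%.

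The moments of ln X among those kept come from numerical integration. All rows:

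| Control (mean, SD) | HMTM (mean, SD) | Lost, control / HMTM | True | Kept, raw scale | Kept, log scale |
|---|---|---|---|---|---|
| 0.5, 1 | 0, 1 | 31% / 50% | 0.50 | 0.32 | 0.27 |
| 0.5, 1 | 0, 0.6 | 31% / 50% | 0.61 | 0.96 | 0.75 |
| 0.5, 1 | 0, 1.5 | 31% / 50% | 0.39 | −0.23 | −0.11 |
| 0.5, 1 | 0.5, 1.5 | 31% / 37% | 0 | not computed | −0.29 |
| 3.0, 1 | 2.5, 1 | 0.1% / 0.6% | 0.50 | 0.49 | 0.45 |

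Simulation with 4 million draws per arm gave log-scale values of 0.271, 0.745, −0.108 and 0.448 for rows 1, 2, 3 and 5. The raw-scale column isolates selection; the last column adds the change of scale. The Baseline covariate and stratification factors of the ANCOVA are left out.

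**The case against.** The best counter-argument is that the visible documents show an undefined outcome, not a wrong one. Section 7.3.5 does not cite Section 4.2, whose formula is labelled relative change rather than percentage change. If the authors meant Week 52 as a percentage of Baseline, the logarithm exists for every positive pair, and that is the more sensible intent. The Secondary Research Plan may say so. No passage says undefined values will be dropped, and a programmer would probably notice them.

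Much of this stands. The link to Section 4.2 is an inference, the selection bias depends on it and on software defaults, and the means and SDs above are invented. The enlarged and reversed results need unequal SDs, which nothing in the documents suggests. The analysis is exploratory.

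It does not remove the point. The wording is log of percentage change, the SAP has only one formula on that scale, and that formula fails for any subject who does not rise. A reader of the SAP cannot recover the ratio reading from the text.

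**Conclusion.** The point holds. As written, the Section 7.3.5 outcome does not exist for any subject whose biomarker is unchanged or lower at Week 52, and the SAP gives no rule for those subjects. That is certain if percentage change means the Section 4.2 formula; only a definition in the unseen Research Plan could displace it.

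If such subjects are dropped, the arm comparison is biased by an amount and in a direction that cannot be predicted without the biomarker means and SDs. The illustrations range from almost no selection effect (0.49 of 0.50 kept) to a reversed sign.

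The reach is limited to this one ANCOVA and its two sensitivity models, for two plasma markers. Section 7.3.4 does not carry it over to the further biomarkers. The Section 7.3.2 ANCOVA on untransformed change still tests the within-group null, and no clinical endpoint is touched.

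**What to change.** In Section 7.3.5, define the outcome of the ANCOVA and both sensitivity models as ln(Week 52 value / Baseline value). It exists for every subject with two positive values. Keep the Section 7.3.2 model otherwise, and report geometric mean ratios, with percent change = 100 × (ratio − 1). If the Secondary Research Plan already defines the outcome, copy that definition into Section 7.3.5 instead.

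The cost is one sentence in the SAP and one line of derivation code. The same edit could settle whether the MRI and PET Baseline values enter separately, as in Section 7.3.2, or in one model, as Section 7.3.5 now reads.

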## Statistical Analysis Plan

Sponsor:	TauRx Therapeutics Ltd.		
Protocol:	TRx-237-039		
Document Version No.:	3.0	Document Date:	07-JUN-2023

### 7.4. Future Sample Analysis

If evidence of a beneficial treatment effect of HMTM is apparent for any of the biomarkers, further analysis at all other timepoints (Week 4 and Week 104) for that biomarker will be performed. In such an event, this analysis will be confirmed by amendment to the biomarker research plan, to the test-site-specific plans, and to this SAP, as appropriate.

If beneficial treatment effect of HMTM is apparent for any of the biomarkers, further sample analysis would be required to show pre-dose and post-dose samples are equivalent for that biomarker.

## Statistical Analysis Plan

Sponsor:	TauRx Therapeutics Ltd.		
Protocol:	TRx-237-039		
Document Version No.:	3.0	Document Date:	07-JUN-2023

### 8. PHARMACOKINETIC EVALUATIONS

A subject data listing with the plasma concentrations (including available modelled parent MT Cmax,ss values) and whole blood concentration data and associated dosing data will be prepared. Calculated values and summary tables will be listed elsewhere.

Statistical Analysis of Pharmacokinetic data will be performed by Certara USA, Inc., and thus its analysis is not within the scope of this SAP but is described elsewhere.

## Statistical Analysis Plan

Sponsor:	TauRx Therapeutics Ltd.		
Protocol:	TRx-237-039		
Document Version No.:	3.0	Document Date:	07-JUN-2023

### 9. ADNI AND META ANALYSIS

Study data will be compared with ADNI (Alzheimer's Disease Neuroimaging Initiative) data and meta-analysis. This analysis is not within the scope of this SAP but is described elsewhere.

## Statistical Analysis Plan

Sponsor:	TauRx Therapeutics Ltd.		
Protocol:	TRx-237-039		
Document Version No.:	3.0	Document Date:	07-JUN-2023

### 10. CHANGES TO PLANNED ANALYSES

The exploratory efficacy F-FDG-PET parameters inferior temporal gyrus and angular gyrus will not be analyzed, since these are included in the lateral temporal cortex and parietal cortex region of interests, respectively.

The exploratory Bayesian analysis, accounting for and using historic data more generally such as placebo decline or treatment effects as priors to inform the analyses of this study, will not be performed.

After the data snapshot (28-APR-2022), the SAP v2.0 signature and the partial study team members unblinding to perform the analysis of the double-blind treatment phase, the version 2.0 of the SAP has been updated to a version 3.0 with added analyses.

Sponsor:	TauRx Therapeutics Ltd.		
Protocol:	TRx-237-039		
Document Version No.:	3.0	Document Date:	07-JUN-2023

## 12. APPENDIX

### 12.1. Considerations regarding COVID-19

This section gives a brief overview of recommendations mentioned therein and their impact to this study regarding its implementation and their applicability. The wording from the guidelines was mostly copied and re-phrased, without changing its essential meaning.

#### 12.1.1. FDA: Statistical Considerations for Clinical Trials During the COVID-19 Public Health Emergency

*In this guideline a change of study conduct, requiring a protocol amendment, is proposed to meet the trial objectives, while prioritizing the safety of (all) study participants:* This was addressed with the protocol version 6.0 with changes as described in Section 2.5, allowing a less stringent conduct (e.g., remote assessment, use of local laboratories).

*Modifications should not be proposed based on data that may introduce bias into the interpretation of trial findings, such as knowledge about magnitude of the treatment effect or information presented by treatment arm:* The changes in study conduct suggest no bias, since they should affect all treatment groups likewise.

*Information at the participant level should be documented, describing the context and/or reasons for post-Baseline events as they relate to COVID-19, such as discontinuation of treatment, withdrawal of the trial, use of alternative or rescue treatments, missed endpoint ascertainment, and the use of alternative endpoint ascertainment methods:* This was addressed with eCRF Covid-19 Impact Assessment and the less stringent conduct (remote assessments, local laboratory). Also, corresponding sensitivity analyses were added (see Section 5.9.2.1).

Considerations with respect to the loss of statistical power due to smaller number of randomized subjects are not needed, since the enrollment of patients or study conduct were not stopped early. To overcome the potential loss of information (more generally) from the impact of COVID-19, the number of randomized subjects was increased with study protocol version 6.0.

*In an event driven trial the follow-up could be extended:* Not applicable.

*Sensitivity analyses should be performed examining differences in Baseline characteristics and post-Baseline events (including endpoints and AEs) between the originally enrolled participants and the additional participants to understand the impact of the change in recruitment, including changes to recruitment locations and time of recruitment:* Considering that most of the subjects under protocol version 5.0 or higher were randomized during COVID-19 and the quite long follow-up time of 12 months, this is not necessary. Furthermore, enrolment was not extended due to COVID-19 per se.

Sponsor:	TauRx Therapeutics Ltd.		
Protocol:	TRx-237-039		
Document Version No.:	3.0	Document Date:	07-JUN-2023

*Closure of a site for a certain period of time could lead to missing endpoint ascertainment, which may not necessarily be related to the treatment assignment or participant characteristics and outcomes. In this case, removing all participants from closed sites who were scheduled for an endpoint ascertainment from the analysis should not bias the findings. It is important to remove all the participants from the closed sites who were scheduled for the ascertainment, regardless of whether they had previously withdrawn. For this approach, the exclusion of participants should not use post-Baseline participant information but instead use only information at randomization (e.g., site location and randomization date). If a significant number of participants are affected, this strategy may result in a significant loss of information: Remote assessment was enabled to minimize missing endpoint ascertainment.*

*Similarly, closure of a site for a certain period of time could greatly impact trial-specified treatment for subjects such that it is unlikely that any treatment effect can be observed, then it may be reasonable to exclude participants who were impacted during that period of time. The decision to exclude subjects should not use post-Baseline subject information (e.g., on-treatment time), but instead use Baseline information (e.g., site location and randomization date).*

*Using alternative ascertainment methods, such as replacing in-person endpoint ascertainment based on performance outcomes or interview-based clinician-reported outcomes with remote ascertainment: Remote assessment and use of local laboratories were established.*

*Extending the protocol-defined window of time for performing the endpoint ascertainment or using an earlier or later planned ascertainment: The study visit windows were extended.*

*For a composite endpoint, including additional and clinically relevant components or removing components that cannot be ascertained: For subitems which could not be assessed by remote, those are reported missing and upscaling will be used. Furthermore, only the subset of items for ADAS-Cog and MMSE, which could be administered remotely (see Section 4.5), will be analyzed in a sensitivity analysis.*

*For a binary endpoint that is based on a continuous or ordinal measurement, using the continuous or ordinal measurement as the endpoint: Not applicable.*

*Evaluation of the impact of any change in endpoint definition or ascertainment, either through a change in methods or a change in timing, should be carefully evaluated in sensitivity analyses. In particular, any differences in the ascertainment between trial arms or among participants with different Baseline characteristics should be explored: The latter is not applicable, since there are no different approaches between trial arms or based on subjects with different Baseline characteristics. Stratified analysis by way of endpoint ascertainment (in-clinic or remote) will be performed in a sensitivity analysis.*

Sponsor:	TauRx Therapeutics Ltd.		
Protocol:	TRx-237-039		
Document Version No.:	3.0	Document Date:	07-JUN-2023

---

